6.2 Exclusion Criteria

Patients will be excluded from the study if they meet **any** of the following criteria:

1. Have a serious concomitant systemic disorder (for example, active infection or a gastrointestinal disorder causing clinically significant symptoms such as nausea, vomiting or diarrhea, or profound immune suppression) that, in the opinion of the investigator, would compromise the patient's ability to adhere to the protocol.
2. Have or known activated/reactivated hepatitis A, B, or C (screening is not required).
3. Uncontrolled human immunodeficiency virus (HIV) infection are considered ineligible. HIV- infected patients on effective anti-retroviral therapy with undetectable viral load within 6 months are eligible for this trial. Known HIV positive patients who meet the following criteria will be considered eligible:
 - a. CD4 count ≥ 350 cells/mm³
 - b. Undetectable viral load
 - c. Maintained on modern therapeutic regimens utilizing non-CYP interactive agents (i.e. excluding ritonavir)
 - d. No history of AIDS-defining opportunistic infections
4. Have symptomatic and untreated central nervous system (CNS) malignancy or metastasis (screening is not required).
 - a. Patients with treated CNS metastases are eligible for this study if they are not currently receiving corticosteroids for their CNS metastasis and/or anticonvulsants. Patient must be > 4 weeks from therapy completion (including radiation and/or surgery) and clinically stable at time of study entry. Brain MRI or head CT is required at screening for patients with known brain metastases.
5. Have current hematologic malignancies, acute or chronic leukemia
6. Have a second primary malignancy that in the judgment of the principle investigator may affect the interpretation of results
7. Have prior malignancies within the last 3 years prior to study enrollment. Patients with carcinoma in situ of any origin and patients with prior malignancies who completed curative intent-treatment and whose likelihood of recurrence is very low, as judged by the principal investigator, will remain eligible for this study. The principal investigator will approve enrollment of patients with prior malignancies in remission before these patients are enrolled.

8. Are currently enrolled in a clinical trial involving an investigational product or any other type of medical research judged not to be scientifically or medically compatible with this study
9. Have participated, within the last 28 days in a clinical trial involving an investigational product.
10. Have previously completed or withdrawn from this study or any other study investigating an ERK1/2 inhibitor.
11. Had prior therapy with an ERK1/2 inhibitor.
12. Had prior chemotherapy within 3 weeks of study registration.
13. Had prior non-CNS radiation within 2 weeks of study registration. Please refer to exclusion criteria #4 for patients who have required radiation for CNS disease.
14. If female, is pregnant, breastfeeding, or planning to become pregnant.
15. Currently using concomitant medications that are strong inhibitors or inducers of CYP3A4.
16. Have serious and/or uncontrolled preexisting medical condition(s) that, in the judgment of the investigator, would preclude participation in this study.
 - a. This includes cardiogenic syncope, ventricular arrhythmias, history of sudden cardiac arrest, or severe dyspnea at rest or requiring oxygen therapy.
 - b. This includes patients with any evidence of interstitial lung disease (ILD) (not just serious and/or uncontrolled ILD) and any history of severe ILD.

6.3 Lifestyle Restrictions

Patients must meet the study entry criteria. There are no additional lifestyle restrictions for participation in Study CTO-IUSCC-0730.

6.4 Screen Failures

Individuals who do not meet the criteria for participation in this study (screen failure) may be re-screened. Individuals may be re-screened one time. Each time re-screening is performed, the individual must sign a new informed consent form (ICF) and will be assigned a new identification number.

Repeating of laboratory tests during the 21-day screening period does not constitute re-screening.

7 Patient Registration

All patients will be registered with the Indiana University Simon Cancer Center (IUSCC) Clinical Trials Office (CTO). Regulatory files will be maintained by the IUSCC CTO. Applicable regulatory documents must be completed and on file prior to registration of any patients. Potential patients will be identified in the Oncology outpatient clinics or by referrals from outside physicians. Patients who appear to be eligible for this trial will undergo the Informed Consent Process and be screened for eligibility utilizing the Eligibility Criteria. The original signed IRB approved Informed Consent Document and completed Eligibility Checklist will be forwarded to the CTO designee for eligibility verification and registration in the

OnCore® database. Notification will be sent to the principal investigator, treating physician and research nurse when registration is complete to confirm registration and inform them of patient ID number.

8 Treatment

The investigator or his/her designee is responsible for the following:

- explaining the correct use of the drugs and planned duration of each individual's treatment to the patients and study site personnel.
- verifying that instructions are followed properly
- maintaining accurate records of study treatment dispensing and collection
- timely reporting of adverse events and product complaints to Lilly
- at the end of the study returning all unused medication to Lilly, or its designee, unless Lilly and sites have agreed all unused medication is to be destroyed by the site, as allowed by local law.

8.1 Treatments Administered

8.1.1 Treatment Plan

8.1.1.1 LY3214996

LY3214996 will be administered at a dose of 200 mg orally once daily on Days 1 through 28 of a 28-day cycle. LY3214996 can be taken with or without food. Doses should be taken approximately the same time each day (\pm 2 hours) as much as possible. If a patient misses or vomits a dose, that dose should be omitted. Treatment will be continued until progressive disease, unacceptable toxicity or patient desire to discontinue study therapy.

8.1.1.2 Abemaciclib

Abemaciclib will be administered at a dose of 150 mg orally Q12 hours (\pm approximately 2 hours) on Days 1 through 28 of a 28-day cycle. During all cycles, abemaciclib should be taken at approximately the same times each day. If a patient misses or vomits a dose, that dose should be omitted. LY3214996 should be taken at the same time as either the a.m. or p.m. dose of abemaciclib.

8.1.2 Packaging and Labelling

LY3214996 and abemaciclib will be provided by Lilly in the United States and will be labeled according regulatory requirements. Lilly will perform the labeling and the final packaging of these study medications under good manufacturing practice (GMP) conditions. All capsules/tablets should be stored according to their associated product label and taken as indicated. Patients should store these agents in the original package provided and according to the product label (where applicable) and be instructed to keep all medications out of reach of children.

8.1.3 Selection and Timing of Doses

A cycle is defined as an interval of 28 days. A delay of a cycle due to holiday, weekend, bad weather, or other unforeseen circumstances will be permitted for a maximum of 7 days and not counted as a protocol deviation. The reason for the treatment interruption should be documented

on the CRF. A cycle begins when study treatment is dispensed for the cycle and administered. Thus, if an expected cycle start is delayed, the number of days in the current cycle is increased beyond 28 days.

A patient may continue to receive study treatment until confirmed progressive disease (Section 10.1), unacceptable toxicity, or discontinuation for any other reason (Section 9).

8.2 Blinding

This is an open-label study.

8.3 Dosage Modification

Please refer to [Appendix 4](#) for dose adjustment guidelines.

Study therapy may be held up to 3 weeks to allow sufficient time for recovery. Patients who do not recover from drug-related toxicity to \leq grade 1 within 3 weeks will be discontinued (except alopecia, fatigue, skin rash, elevated creatinine, nausea, vomiting, constipation or diarrhea that can be controlled with treatment). If a dose adjustment is made, the patient must be maintained at the reduced dose level for all remaining cycles.

For the purposes of dose modification, the investigator must first assess if the toxicity is considered at least possibly due to one of the study drugs, and must then apply the study drug-specific dose-modification guidelines accordingly. If the toxicity is not clearly attributable to either individual study drug, then the causality should be attributed to both study drugs. Dosing interruptions of any study drug are permitted for reasons not related to study treatment (for example, minor surgery, unrelated medical events, patient vacation, and/or holidays). The reason for interruption should be documented on the CRF.

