Appendix 4. Dose Modification of LY3214996 & Abemaciclib

Neutropenia	Abemaciclib	LY3214996
≤ Grade 1/2	No change in dose.	No change in dose.
Grade 3	Hold* until ≤ Grade 2. Resume at same dose level.	No change in dose.
Recurrent Grade 3 or Grade 4	Hold* until ≤ Grade 2. Reduce by 1 dose level.	No change in dose.

*Patients requiring a delay of all protocol therapy > 3 weeks due to toxicity should go off protocol therapy.
 
NOTE: Use of prophylactic granulocyte colony stimulating factor is permitted per investigator discretion. Use of ASCO guidelines is recommended. Suspend therapy for at least 48 hours after the last dose of a blood cell growth factor was administered and until toxicity resolves to at least Grade 2.
		

Abbreviation: ASCO = American Society of Clinical Oncology

Thrombocytopenia	Abemaciclib	LY3214996
≤ Grade 1/2	No change in dose.	No change in dose.
Grade 3	Hold* until ≤ Grade 2. Resume at same dose level.	No change in dose.
Recurrent Grade 3 or Grade 4	Hold* until ≤ Grade 2. Reduce by 1 dose level.	No change in dose.

*Patients requiring a delay of all protocol therapy > 3 weeks due to toxicity should go off protocol therapy.
		

Anemia	Abemaciclib	LY3214996

Supportive transfusion is permitted after cycle 1, day 1 and future cycles for subjects who do not meet hemoglobin parameters for retreatment.
		
Hemoglobin	Abemaciclib	LY3214996
Grade 1/2	No change in dose	No change in dose.
Grade 3	Hold* until ≤ Grade 2. Resume at same dose level.	No change in dose.
Recurrent Grade 3 or Grade 4	Hold* until ≤ Grade 2. Reduce by 1 dose level.	No change in dose.
Patient requires administration of a blood cell growth factor	Suspend abemaciclib dose for at least 48 hours after the last dose of blood cell growth factor and until toxicity resolves to ≤Grade 2. Resume abemaciclib at next lower dose unless the dose was already reduced for the toxicity that led to the use of the growth factor.	No change in dose.

*Patients requiring a delay of all protocol therapy > 3 weeks due to toxicity should go off protocol therapy. Supportive transfusion is permitted after cycle 1, day 1 and future cycles for subjects who do not meet hemoglobin parameters for retreatment.
		

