Recurrent in the context of dose interruptions and delays refer to the same event occurring within the next 8 weeks (as measured from the stop date of the first event). This does not include events in the same class (for example, neutropenia followed by anemia 1 month later).

As a general approach, based on the **risk/benefit balance assessment per the investigator**: for a patient who experiences a new episode of Grade 3 hematological toxicity after more than 8 weeks following the last episode of **same** Grade 3 hematological toxicity, the investigator may consider resuming the patient on the same drug dose if the patient satisfies the following conditions:

- The patient showed stable hematological counts (\leq Grade 2) during that time frame
- In the absence of any infectious sign or risk factor
- The patient is getting benefit from study treatment.

Non-Hematologic Toxicity:

Nausea**	Abemaciclib	LY3214996
\leq Grade 1	No change in dose.	No change in dose.
Grade 2	Hold* until \leq Grade 1. Resume at same dose level.	Hold* until \leq Grade 1. Resume at same dose level.
Grade 3	Hold* until \leq Grade 1. Reduce by 1 dose level.	Hold* until \leq Grade 1. Reduce by 1 dose level.
*Patients requiring a delay of all protocol therapy > 3 weeks due to toxicity should go off protocol therapy. ** After optimal anti-emetic therapy. Please refer to Section 8.6.1 . Use of prophylactic or scheduled antiemetics are recommended in future cycles for patients experiencing grade 2 or higher nausea.		

Vomiting**	Abemaciclib	LY3214996
\leq Grade 1	No change in dose.	No change in dose.
Grade 2	Hold* until \leq Grade 1. Resume at same dose level.	Hold* until \leq Grade 1. Resume at same dose level.
Grade 3	Hold* until \leq Grade 1. Reduce by 1 dose level.	Hold* until \leq Grade 1. Reduce by 1 dose level.
Grade 4	Hold* until \leq Grade 1. Reduce by 1 dose level.	Hold* until \leq Grade 1. Reduce by 1 dose level.
*Patients requiring a delay of all protocol therapy > 3 weeks due to toxicity should go off protocol therapy. ** After optimal anti-emetic therapy. Please refer to Section 8.6.1 . Use of prophylactic or scheduled antiemetics are recommended in future cycles for patients experiencing grade 2 or higher vomiting.		

Diarrhea**	Abemaciclib	LY3214996
≤ Grade 1	No change in dose.	No change in dose.
Grade 2 (1st episode)	Hold* until ≤ Grade 1. Resume at same dose level.	Hold* until ≤ Grade 1. Resume at same dose level.

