Ask your patients to report any new or worsening respiratory symptoms such as cough, dyspnea, fever, and investigate and treat as per your local clinical practice, including corticosteroids as appropriate. If interstitial lung disease/pneumonitis is suspected, investigations may include imaging, such as high-resolution CT scans, bronchoalveolar lavage, and biopsy as clinically indicated. Please refer to dosing guidelines below for respiratory toxicity.

ILD/Pneumonitis	Abemaciclib	LY3214996
≤ Grade 1	No change in dose.	No change in dose.
Grade 2 (>7 days despite maximal supportive measures or recurrent)	Hold* until ≤ Grade 1 or baseline. Reduce by 1 dose level.	Hold* until ≤ Grade 1 or baseline. Resume at same dose level.
Grade 3/4	Discontinue therapy.	Discontinue therapy.
*Patients requiring a delay of all protocol therapy > 3 weeks due to toxicity should go off protocol therapy.		

Cutaneous toxicity should be managed per guidelines in [Section 8.6.1.1](#). In the event of grade 3 or higher dermatologic toxicity, hold abemaciclib and LY3214996 until dermatologic toxicity resolves to ≤ grade 2 or pre-treatment baseline. Subsequent LY3214996 treatment should be dose reduced by one dose level. Abemaciclib does not require dose reduction. Treatment may be held for up to 21 days. If the toxicity is not improved to ≤ grade 2 or pre-treatment baseline within the 21-day period, the patient will discontinue therapy. Additionally, a one level dose reduction of LY3214996 is permitted for intolerable grade 2 dermatologic toxicity, at the discretion of the treating physician. Such dose reductions should be undertaken in conjunction with management of cutaneous toxicity as described in [Section 8.6.1.1](#).

For any grade 3 or 4 toxicity, not mentioned above, the treatment should be withheld until the patient recovers to grade 1 or less toxicity. The treatment may then be resumed at one dose level reduction. For intolerable grade 2 toxicities, withhold treatment until the patient recovers, then resume treatment at a one dose level reduction. Dose reduction will be done for the drug that is most likely to have caused the toxicity. For grade 1 or tolerable grade 2 toxicities or clinically insignificant laboratory changes, no dose reduction should be made.

Dose adjustments as outlined in the table below are allowed both within a cycle and between cycles for abemaciclib. Abemaciclib must be reduced sequentially by 1 dose level.

Dose Adjustment	Oral Dose	Frequency

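### For neutropenia, thrombocytopenia and anemia, Section 8.3 and Appendix 4 contradict each other on who stops treatment after a three-week toxicity hold

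*Combined protocol and SAP*

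**What the plan says.** Section 8.3 refers to Appendix 4 for dose adjustment and then sets its own limits. It first caps the hold: "Study therapy may be held up to 3 weeks to allow sufficient time for recovery". It then says that patients whose drug-related toxicity has not recovered to at most "grade 1 within 3 weeks will be discontinued (except alopecia, fatigue, skin rash, elevated creatinine, nausea, vomiting, constipation or diarrhea". The parenthesis ends with "that can be controlled with treatment", a phrase the protocol does not define.

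Appendix 4 works by toxicity:

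- **Grade 3 neutropenia, thrombocytopenia or anemia.** The abemaciclib column reads "Hold* until ≤ Grade 2. Resume at same dose level". Recurrent Grade 3 or Grade 4 has the same recovery grade, with a dose reduction. LY3214996 is unchanged throughout.
- **Three-week footnote**, under these tables and under those for nausea, vomiting, diarrhea, AST/ALT and ILD: "Patients requiring a delay of all protocol therapy > 3 weeks due to toxicity should go off protocol therapy".
- **Nausea, vomiting and diarrhea.** From Grade 2 upward both drugs are held to Grade 1. Events are graded after supportive treatment (for nausea and vomiting, "After optimal anti-emetic therapy").
- **Skin toxicity.** From Grade 3 upward both drugs are held. If there is no improvement to Grade 2 or "pre-treatment baseline within the 21-day period, the patient will discontinue therapy".

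**The concern.** Both texts are worded as instructions on whether a patient stays on treatment, and they use different recovery grades (1 against 2) for the same cytopenias. They also attach the three-week limit to different things: Section 8.3 to the patient's recovery, Appendix 4 to a delay of both drugs together. An investigator who follows one text can be recorded as deviating from the other under Section 13.7.

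The first consequence is for safety and consistent conduct. Exposure may continue where one section says stop, or end where the other says continue. There are also effects on the data. The rule chosen can change the recorded reason for discontinuation (Section 14.3.2.3) and whether a patient reaches the first on-treatment scan at cycle 3. It can also change what is observed for PFS and duration of response, because Section 9.4 follows patients only to the 30-day safety visit.

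**Working it through.** The plan gives no figure on this point, so the check sets the two rules side by side. Take a patient with a drug-related toxicity at day 21 of a hold.

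- Section 8.3: stop if the grade is above 1 and the toxicity is not exempt.
- Appendix 4: stop if the grade is above the table's recovery grade and all protocol therapy is delayed beyond three weeks.

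| Status at day 21 | Section 8.3 | Appendix 4 | Agreement |
|---|---|---|---|
| Cytopenia, Grade 1 or less | stays | stays | yes |
| Cytopenia, Grade 2 | stopped | abemaciclib resumes, LY3214996 unchanged | **no** |
| Cytopenia, Grade 3, LY3214996 continued | stopped | stays on LY3214996 | **no** |
| Cytopenia, Grade 3, both drugs suspended throughout | stopped | off once the delay passes 3 weeks | yes |
| Nausea, vomiting or diarrhea, Grade 2 or more | stays if counted as controllable | off once the delay passes 3 weeks | depends on the undefined phrase |
| Rash, Grade 3 | stays if counted as controllable | off | depends on the undefined phrase |
| Rash, Grade 2 or less (exemption taken to apply) | stays | stays | yes |
| AST/ALT after a Grade 3 event, still above Grade 1 | stopped | off | yes |
| ILD after a Grade 2 event, still above Grade 1 and baseline | stopped | off | yes |

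Fatigue and raised creatinine fall under Appendix 4's general rule for other Grade 3 or 4 toxicity. That rule repeats no three-week limit, so no direct contradiction is shown.

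**Does the Grade 2 row depend on how Section 8.3 is read?** Suppose its limit runs only while both drugs are held. Appendix 4's neutropenia note on growth factors suspends therapy until Grade 2. A neutropenic patient at Grade 2 on day 21 with both drugs suspended would then restart under Appendix 4 once the 48-hour growth-factor interval has passed, and would still be stopped under Section 8.3. For neutropenia the thresholds conflict on either reading.

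**Frequency.** The relevant quantity is the share of patients with a Grade 3 or worse cytopenia that remains above Grade 1 at three weeks. The documents do not give it. The nearest figures are:

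- Table 3.2, Part C (LY3214996 plus abemaciclib): related anemia of any grade 5/20 = 25%, Grade 3 or worse 0/20. A zero count in 20 does not show absence: the exact one-sided 95% upper limit is 1 − 0.05^(1/20) = 0.139.
- Table 3.1: one Grade 3 anemia/thrombocytopenia DLT, at LY3214996 200 mg twice daily, which is not this trial's schedule.

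**Design quantities.** With 28 patients and success at 4 or more responses, P(X ≥ 4 | 5%) = 0.0491 and P(X ≥ 4 | 19%) = 0.8065, and 28/(1 − 0.20) = 35. These match Section 14.1. The ORR denominator is all treated patients (Section 14.3.2.1), so neither stopping rule enters these figures.

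**The case against.** Four arguments can be made against the point.

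1. **The specific text governs the general one.** Section 8.3 sends the reader to Appendix 4 and tells the investigator to apply the drug-specific guidance. That pointer exists, but it covers dose modification. Section 8.3 then states a separate discontinuation rule in mandatory terms, and nothing says that the appendix overrides it.

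2. **Appendix 4's three-week footnote still protects patients with cytopenias.** A reader might infer that it can never operate for them because LY3214996 continues. The documents do not support that. Sections 8.6.1 and 8.6.1.4 hold both drugs when growth factors are needed, so all therapy can be delayed. This removes the conflict only for a patient at Grade 3 with both drugs held throughout. It leaves the Grade 2 case, and the Grade 3 case with LY3214996 continued.

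3. **The rash and gastrointestinal conflict may be only apparent.** An event still at Grade 2 or worse after optimal supportive treatment is hard to call controlled, so both texts could be read as stopping the patient. Section 8.3's cap on the length of a hold also carries no exemption. Exempting rash from recovery to Grade 1 is compatible with Appendix 4's Grade 2 threshold. This argument largely stands. What remains is that the phrase is undefined and that it is unclear whether it qualifies the whole list or only its last item.

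4. **Section 9.1 counts a patient as discontinued only when all study treatments have stopped.** It permits single-drug continuation, but it does not say whether Section 8.3's limit runs on one drug or on both.

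**Conclusion.** The contradiction is real for neutropenia, thrombocytopenia and anemia: at Grade 2 on day 21, and at Grade 3 where LY3214996 has continued. This assumes that the toxicity is drug-related and that Section 8.3 means what it literally says about recovery to Grade 1. For rash, nausea, vomiting and diarrhea there is an ambiguity that turns on an undefined phrase. The two texts do not disagree across all toxicities.

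The size in patients is unknown. A reader might apply the abemaciclib monotherapy rates in Section 3.1.2.1.1 to 28 patients: 28 × 0.371 = 10.4 with neutropenia, 28 × 0.250 = 7.0 with anemia, 28 × 0.205 = 5.7 with thrombocytopenia. Those rates are for any grade at 200 mg twice daily in breast cancer, so they do not count patients caught between the two rules.

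A reader might also infer a threat to the primary test, because one lost responder can turn 4 of 28 into 3, and P(X ≥ 3 | 5%) = 0.163 against 0.049. Any cause of a lost responder does the same, so this does not measure the defect. The case for acting rests on patient safety and consistent conduct.

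**What to change.** Reconcile Section 8.3 with Appendix 4 so that, for each toxicity class:

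- one recovery threshold applies, with or without return to baseline as an alternative;
- one three-week rule applies, stating whether it runs when either drug is held or only when both are;
- the phrase about control with treatment is defined, with its reach over the list made clear, or removed.

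Add a sentence saying which text governs discontinuation. Which thresholds and limits to adopt is for the sponsor's medical team.

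The cost is a wording amendment to Section 8.3 and the Appendix 4 tables and footnotes. It needs no new procedures, no extra patients and no change to the statistical design.
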